8.3 Storage and delivery of the study drug

The drug will be stored in the pharmacy or in another safe place at the study centre, at a temperature below 30°C. The drug must be kept in its original packaging to protect it from direct light. One capsule of cetirizine/placebo will be administered one hour before the IFNβ injection.

At visit V1, the Investigator shall give each patient the box showing the patient's randomisation number and the words: FIRST MONTH, containing a sufficient number of capsules to cover the number of Interferon injections to be given at the highest administration frequency (14 injections/month), and shall explain the administration and storage method. At visit V2, the Investigator shall collect the unused drug and the used blister cards and give the patient the box coded with the same randomisation number and the words SECOND MONTH. When dispensing the drug packages, the Investigator shall note the date of delivery and quantity of drug dispensed in the medical record and the Case Report Form. In addition, the date and quantity of the drug provided to each patient must be recorded on an accounting form provided by the selected CRO. At visit V3 the patient must return the previously received packages to the Investigator, whether

used or not. These packages shall then be sent to the Sponsor who shall ensure that they are destroyed.

Each patient will be given a diary in which he/she must record the dates on which the drug was taken. The Investigator shall check compliance at the visits specified by the protocol.

The Investigator shall record the date the drug is returned by the patient and the number of unused capsules in the accounting form.

8.4 Randomisation procedure

When entering data into the centre's database, the patient will be automatically assigned a "Unique Code for Trial Subject (UCTS)" and a "Personal Identity Code (PIC)" which will clearly identify the case during the Study, at the same time as guaranteeing absolute anonymity and protection of the patient's identity. After verification of the inclusion/exclusion criteria (V1), the UCTS and PIC codes will be confirmed or, if the patient does not meet the criteria, they will be entered into the screening failure list. A randomisation number (RN) of 01 to 40 will be assigned at the time of randomisation, and linked to the PIC and will coincide with the number shown on the drug used by the patient.

During the study each patient will thus be identified by the Unique Code for Trial Subject (UCTS), the Personal Identification Code (PIC) and the RandCod (Randomisation Code, formed by the combination of PIC+RN), coinciding with the number on the assigned drug. The two codes (PIC+RN) will create the Randomisation Code, which will be shown on the questionnaire and patient diary.

Assignment of the UCTS, PIC, RN and RandCod is fully automated and does not require operator intervention.

This is a double-blind crossover study; all participating patients will therefore receive both cetirizine and the placebo according to a completely randomised sequence.

The randomisation list will cross over every 4 subjects and will be prepared by IBIS using the Nquery programme. This list will be held in a password protected PDF file, transferred to an electronic medium (CD/DVD/USB drive) and sent to the packaging manager of the Officina Farmaceutica Corden Pharma SpA by courier. The password to open the file will be sent separately. One copy of the list will be filed under the responsibility of the Scientific Director of IBIS Srl. Until the study is unblinded, only the Scientific Director of IBIS, the packaging manager for Corden Pharma SpA and their immediate colleagues may know the contents of the list.

Once the Sponsor authorizes the unblinding of the study, the list will be sent to both the IBIS biometry unit and to the Sponsor itself.

8.5 Blinding

This is a randomised, double-blind, crossover study. The investigators and the staff at the study centre, the Sponsor and the CRO will be blinded to the patient sequence for the entire duration of this Study. The Investigator will be given a closed and sealed envelope at the same time as the drug, containing the name of the drug (cetirizine or placebo) administered in the respective

sequence in order to be able to address any safety needs that may require the drug taken during the investigational therapy cycle to be known. The opening of this envelope must be authorized by Biogen Idec Italia Srl's Pharmacovigilance Unit and suitable justification provided in the e-CRF.

At the end of the research, all the open or still-sealed envelopes must be collected by the Clinical Monitor and filed in the Trial Master File (TMF).

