8.2 Identity of the study products

8.2.1 Packaging and labelling

Cetirizine, purchased from Farmacie Celesia S.r.l., is supplied as over-encapsulated tablets to be taken orally, in blister packs each containing 6 capsules. Each cetirizine tablet contains 10 mg of active ingredient.

The placebo is also encapsulated in capsules that are indistinguishable from those used for the cetirizine; these are also packaged in blister cards containing 6 tablets each.

The following shall appear on each blister pack:

Biogen Idec Italia S.r.l. - Study: BIIT 0212

Randomisation number

Batch number

First/Second month of treatment

Expiry date

The drug will be contained in two separate boxes to be given to the patient at the follow-up visits, each containing 3 blister cards for a total of 18 capsules of cetirizine or placebo, according to a randomisation list.

The following specifications will be shown on each box:

Biogen Idec Italia S.r.l. - Study: BIIT 0212

Randomisation number

First month of treatment or second month of treatment

Batch number

Expiry date

Store at a temperature below 30°C

"FOR CLINICAL TRIALS ONLY"

"Return the remaining capsules and used blister cards at the next follow-up visit"

"Keep out of the reach of children"

"Avoid release to the environment"

Lastly, the two boxes will in turn be placed into one box which will remain in the possession of the Investigator and which will be collected at the end of the study with the remaining drug to be disposed of.

The following specifications will be shown on these boxes:

Biogen Idec Italia S.r.l. - Study: BIIT 0212

Randomisation number

Batch number

Expiry date

Store at a temperature below 30°C.

"FOR CLINICAL TRIALS ONLY"

Each patient will be given a card to be kept with him/her at all times that shows: the name of the Investigator, the title of the study in which he/she is enrolled and the telephone number to call if needed.

The company appointed by Biogen Idec Italia S.r.l. to package, label and distribute Cetirizine to the Trial Centre is IBIS Informatica Srl, which has nominated Corden Pharma S.p.A., [name], which meets the legal requirements, and which will provide the certification to release the investigational drug in accordance with applicable laws, as the site responsible for preparing the boxes of drugs for patients and their logistics.

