14.1 Study authorisation

All documentation relating to amendments to the Study Protocol, adverse events and suspension of the Study must be sent to the Ethics Committee exclusively via the CRO.

All expenses connected with submission of the documents and the approval procedures or the presentation of Protocol amendments to the Ethics Committee will be at the exclusive expense of the CRO.

The study centre will not alter or modify the Protocol nor permit the PRINCIPAL INVESTIGATOR or any member of the staff to alter or modify the Protocol in any way without the express written consent of Biogen Idec Italia and the approval of the competent Ethics Committee, unless required by law for the purpose of protecting the health, safety or rights of the Subjects.

According to the provisions of Legislative Decree 211 of 24 June 2003 (Official Gazette No. 184 of 9 August 2003), the Protocol must be submitted to the Ethics Committee which, in the case of monocentric trials, must communicate its reasoned opinion to the sponsor, the Minister of Health and the competent authorities within 60 days of receiving the application presented by Biogen Idec Italia.

During the period in which the application is being examined, the Ethics Committee may submit a one-time-only request for additional information to Biogen Idec.

The Study may commence at the research centre only upon written approval by the Ethics Committee, signing of the financial agreement with the centre, and issuance of the relevant Administrative Resolution.

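### Section 8.5 gives the investigator a code-break envelope for safety needs but makes opening it depend on sponsor authorisation, with no exception for urgent cases

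*Protocol*

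**What the plan says.** Section 8.5 states that the investigators, site staff, sponsor and CRO "will be blinded to the patient sequence for the entire duration of this Study". It then makes one provision for breaking the code: "The Investigator will be given a closed and sealed envelope at the same time as the drug". The envelope names the treatment, and its purpose is given as "in order to be able to address any safety needs that may require the drug taken during the investigational therapy cycle to be known".

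The next sentence sets the condition: "The opening of this envelope must be authorized by Biogen Idec Italia Srl's Pharmacovigilance Unit". A justification must also be entered in the e-CRF. At the end of the study all envelopes, opened or not, go to the Trial Master File.

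Section 8.4 restricts the randomisation list. Until unblinding, "only the Scientific Director of IBIS, the packaging manager for Corden Pharma SpA and their immediate colleagues may know the contents of the list".

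**The concern.** An envelope is kept at the site so that the treatment can be identified quickly. Making its opening depend on a decision by a sponsor unit elsewhere can take away that speed in the situation the envelope is for. Section 8.5 does not say what the investigator should do if the treatment has to be known before the unit has answered. Read literally, the investigator waits.

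What is at stake is a possible delay in identifying the treatment in an emergency. The need is not remote from this trial. Section 8.9 lists convulsions, syncope and Quincke's edema among the effects observed or reported with cetirizine. Patients take the capsules between visits four weeks apart, so an event can occur at any hour. The statistical results are not at stake.

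**Working it through.** No calculation decides this point. The check is whether any other part of the protocol supplies the exception that 8.5 lacks.

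1. **Purpose against condition (8.5).** The purpose is "in order to be able to address any safety needs". The condition is authorisation by the sponsor's pharmacovigilance unit plus a written justification. The condition is worded without exception. It sets no response time, names no deputy and does not allow opening first and reporting afterwards.

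2. **Second route to the allocation (8.4).** The list is confined to the CRO's scientific director, the packaging manager and their close colleagues. The investigator is not among them, and the section describes no emergency request to them.

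3. **Patient card (8.2.1).** The card shows the investigator's name, "the title of the study in which he/she is enrolled and the telephone number to call if needed". Nothing links that number to code-breaking.

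4. **SAE reporting (2.2 and 9.6).** Section 2.2 sets one business day (24 hours). Section 9.6 sets 24 hours, by fax or e-mail. Both concern reporting to the sponsor; neither mentions unblinding.

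5. **Safety exception (14.1).** The bar on altering the protocol without the sponsor's written consent and ethics approval is lifted "unless required by law for the purpose of protecting the health, safety or rights of the Subjects". This concerns changes to the protocol and does not mention the envelope.

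So the text visible in the protocol contains no exception. The two sentences of 8.5 can both be followed whenever authorisation arrives in time, and they conflict when it does not.

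**Scale.** If all patients complete, follow-up is 40 patients × 8 weeks = 320 patient-weeks, half of it on cetirizine (160). The protocol gives no rate for events that would call for unblinding, so the expected number of such cases cannot be derived.

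**What one opening reveals.** With two treatments in two periods, knowing the drug in one period gives the drug in the other. Section 8.4 says the list crosses over every 4 subjects. Assume this means blocks of 4 with two patients per sequence. Once one patient's sequence is known, the other three places in the block hold one patient on the same sequence and two on the opposite one. A guess of the opposite sequence for any of those three is then right with probability 2/3, against 1/2 without the information. This matters only if the site knows the block size.

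**The case against.** The strongest reply is that the section states a purpose and a control, and the two normally coexist. The envelope is already in the investigator's hands, so one successful contact with the unit is enough to open it. A reader might infer that the envelope cannot serve its purpose at all, or that the two sentences contradict each other outright. The text does not support that: the failure is conditional on authorisation not arriving in time.

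A reader might also infer that the unit cannot be reached out of hours. That cannot be concluded either. Contact details are removed from the public copy, and any out-of-hours or back-up arrangement could have stood there.

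It can be said that authorisation might be given afterwards, since the sentence fixes no timing. Permission before opening is the natural reading, and an investigator under time pressure could not safely assume another. It can also be said that 14.1, together with the commitment in section 14 to good clinical practice and the Declaration of Helsinki, gives some cover. These are general provisions and do not state a rule for the envelope.

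Finally, prior authorisation does protect the blind. It would be wrong to claim that notification after opening protects it equally well. The primary measure is a subjective VAS, and one opening discloses both of a patient's periods. That objection stands, and it is why prior authorisation should stay for non-urgent requests.

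**Conclusion.** The point holds in limited form. Section 8.5 states a rule without an urgent-case exception, and the rule defeats the envelope's stated purpose only when the treatment must be known before authorisation can be obtained. That is likely rare in a trial of this size and length. The protocol sets no limit on how long authorisation may take, but this does not show that a long delay is likely.

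The conclusion rests on two assumptions: that the sentence means authorisation before opening, and that the removed text contains no exception. The unit's actual availability is unknown and is not part of the finding.

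This is a cheap improvement on patient-safety grounds. It has no effect on power or type I error.

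**What to change.** Reconcile the two sentences in 8.5:

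- In an urgent safety case, opening the envelope does not depend on prior authorisation by the sponsor. The investigator notifies the sponsor immediately and enters the e-CRF justification that 8.5 already requires.
- For non-urgent requests, prior authorisation by the pharmacovigilance unit remains.
- The final report lists every opened code.

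The change is about one sentence in 8.5 and a line in the report. Its downside is a slightly higher chance of an unnecessary unblinding. Each such case discloses both periods for that patient and may sharpen guesses about others in the same block if the block of 4 is known at the site. The e-CRF justification and the collection of all envelopes at the end of the study remain as checks on this.

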8.6 Adherence to the treatment

At visits V2, V3 and in the event of a drop-out, Vx, the Investigator shall check the patient's compliance with treatment by examining the quantity of drug contained in the packages that the patient returns and the quantity reported in the diary.

Any discrepancy between the expected quantity and the quantity actually used shall be a measure of the patient's compliance with the prescribed posology; this information will be noted on the e-CRF.

8.7 Previous treatments and concomitant therapies

All treatment being received for RRMS must be documented in the e-CRF, including the current one.

Concomitant treatments for RRMS, such as symptomatic treatments, or treatments for other pathologies, may be used at the Investigator's discretion. Any changes to concomitant therapies must be reported in the e-CRF. If the patient is already taking drugs for the treatment of FLS, for example paracetamol or ibuprofen, considered as being the standard of therapy (SOT), they must continue to maintain the dose of that therapy as stable as possible during the study period, at the discretion of the Investigator and in accordance with standard clinical practice.

8.8 Special warnings and precautions for using the study drug

The elimination of Cetirizine may be compromised in patients with renal and liver failure. Caution should be taken in the administration of Cetirizine to these patients. Cetirizine may increase the effects of alcohol and depressants that act on the central nervous system. Therefore, caution is recommended in the assumption of alcohol and central nervous system depressants during the study.

Cetirizine may have a minimal or moderate influence on the patient's reactions. This must be taken into consideration when particular vigilance is needed, for example when driving.

The study product contains lactose monohydrate. Patients with rare hereditary galactose intolerance problems, Lapp lactase deficiency or glucose-galactose malabsorption should not take the medicinal product.

Data on a limited number of exposures to the drug during pregnancy suggest Cetirizine has no adverse effects on pregnancy or on the health of the foetus or newborn baby. Data on the excretion of Cetirizine in human milk are not available.

8.9 Side effects of the study drug

Taking Cetirizine may be associated with dry mouth, headache, dizziness, sleepiness, agitation, and abdominal and digestive disorders. Reversible disorders related to liver function, epileptic convulsions, thrombocytopenia, palpitations, tachycardia, syncope and weight gain have been observed. Rare cases of allergic reactions such as skin reactions and Quincke's edema have been reported.

9 PHARMACOVIGILANCE

9.1 Definitions

9.1.1 Adverse event

Adverse event (AE): any unfavourable medical event (signs, symptoms and abnormal laboratory results) occurring in a patient or in a subject participating in a clinical trial who has been given a pharmaceutical product, which does not necessarily have a causal relationship with the treatment.

AE intensity.

This is a subjective evaluation. The Investigator will use his or her own judgment to compare the adverse event with other similar events occurring in clinical practice. The intensity of any AE will be evaluated according to the following criteria:

- Mild: not causing limitation in normal activities. Subjects may complain of minor disorders.
- Moderate: causing certain limitations in normal activities. Subjects may complain of unpleasant disturbances.
- Severe: causing inability to carry out normal activities. Subjects may complain of unbearable disturbances or pain.

9.1.2 Serious adverse event

An SAE is any AE that:

- is fatal;
- poses a threat to life;
- requires hospitalisation or extends a current hospitalisation;
- leads to disability/continuing or significant incapacity;
- causes birth defects or congenital abnormalities;
- is a clinically significant medical event.

N.B.: the severity of an adverse event is not necessarily determined by its intensity. For instance, moderate nausea leading to hospitalisation shall be considered as serious.

9.2 Recording

Any data on adverse events (both serious and non-serious) occurring during the study must be collected and recorded in the e-CRF. It is essential to record the duration of any adverse event (onset and resolution date), its correlation with the drug, its outcome, and concomitant treatments, if any.

9.3 Correlation judgement

When making a judgement about correlation with the drug, the Investigator will consider the patient's clinical condition, concomitant therapies and the temporal relationship between the onset of the event and the administration of the investigational treatment. For every adverse event, the Investigator shall express a judgement on the possibility that the event can be plausibly correlated with the drug administered or not.

9.4 Adverse Drug Reaction (ADR)

Any harmful and unwanted response to a medicinal product occurring at a dose that is normally administered in humans for the prophylaxis, diagnosis or treatment of diseases, or to modify physiological functions.

The phrase "response to a medicinal product" means that the causal relationship between the AE and the medicinal product is at least a reasonable possibility, i.e. that such a relationship cannot be excluded. Therefore, in contrast to an AE, an ADR is characterised by the fact that a causal relationship between the AE and the medicinal product is considered at least possible.

9.5 Unexpected Adverse Drug Reaction

Any ADR whose nature and intensity do not correspond to the available information about the product (Summary of Product Characteristics or Investigator's Brochure).

9.6 Notification of serious adverse events

The Investigator shall immediately report every SAE to the Biogen Idec pharmacovigilance manager and in any event within 24 hours of the event occurring or being made known to the Investigator by fax or e-mail using Biogen Idec's SAE form. Any event follow-up shall be reported to the Biogen Idec Pharmacovigilance manager within 24 hours.

The contact details of the Pharmacovigilance manager are the following:

[name]

Senior Associate I, Drug Safety

Biogen Idec Italia S.r.l.

[name]

[contact] - [contact]

[contact]

E-mail: [contact]

10 DATA MANAGEMENT AND STATISTICAL ANALYSIS

10.1 Data management

Study data will be recorded in the e-CRF, in electronic format, linked via the Internet to a central database. The Investigator will use the e-CRF in Italian to record patient data, collected by the patient in the original documentation. The Investigator will be able to access the e-CRF directly on the computer (after installation); no other technical support will be provided. The Investigator (and co-Investigators, where applicable) and the Clinical Monitor will have direct access to the e-CRF on the Investigator's computer using their own Login and password. The Clinical Monitor, the Sponsor and the Data Manager will also have access to the central database on the reference site using their individual Login and Password. Every access and/or modification to the local e-CRF and the central database will be tracked on a LOG file, available for consultation upon request. In order to ensure protection of the data recorded by each investigator, every user will be provided with individual access. Monitoring will be carried out by Clinical Trial Consulting ss staff on behalf of IBIS (CRO), designated by the Sponsor. Questionnaires will be checked by the CRO Monitor designated by the Sponsor during the scheduled monitoring visits at the centre, as an integral part of the centre's original documentation (e.g. clinical files, laboratory examination and radiology results etc.) who will also verify whether the Investigator has correctly entered the questionnaire and diary data into the e-CRF. When requests are made for support relating to entering data into the e-CRFs. the Investigator may contact the CRO at: [contact]; email: [contact].

Compliance with applicable regulations on personal data protection will be ensured, in particular Legislative Decree no. 196 of 30 June 2003 and the Guidelines for the Guaranteeing of the protection of personal data – resolution no. 52 del 24/07/2008.

